This is a prospective, randomized single-center phase III pilot clinical trial comparing recombinant von Willebrand factor (rVWF, Vonvendi®) plus tranexamic acid (TA, Cyclokapron®) vs. rVWF alone to reduce postpartum hemorrhage (PPH) in women with von Willebrand disease (VWD). We *hypothesize* that intravenous rVWF given just before delivery plus intravenous tranexamic acid within 3 hours of delivery is superior to rVWF alone in reducing postpartum blood loss.

Objective:

The **Primary Objective** is to determine the efficacy of rVWF plus TA vs. rVWF alone in reducing postpartum hemorrhage in women with VWD.

The **Secondary Objectives** are to evaluate safety, tolerability, and mechanism of rVWF plus TA vs. rVWF alone in reducing PPH in women with VWD.

Endpoints:

The **Primary Endpoint** is quantitative blood loss (QBL) calculated by a labor suite nurse at delivery. The **Secondary Endpoints** include safety assessment by lochial blood loss by pictorial blood assessment chart (PBAC), blood products, transfusion, and hysterectomy within 21 days of delivery; and mechanism of PPH reduction by VWF assays, fibrinogen, and d-dimer.

Study Population:

Study subjects will be females age \geq 18 years of age with von Willebrand disease, defined by VWF:RCo <0.50 IU/dL (historic) and previous bleeding history, undergoing vaginal or caesarean section delivery. A total of 20 eligible subjects with VWD will be enrolled in this 2-year trial.

Site Enrolling Subjects:

Pilot: Participating site is HCWP, and Magee Hospital obstetricians.

Description of Study Intervention:

There are two study interventions: rVWF plus tranexamic acid vs. rVWF alone. Recombinant von Willebrand factor (rVWF, Vonvendi®) is an FDA-approved clotting factor approved for treatment or prevention of bleeds including postpartum hemorrhage hemorrhage in VWD. It is an intravenous agent administered in single-use vials containing approximately 650-1300 IU per vial as a sterile, lyophilized powder. The vials are reconstituted with 5-10 ml vial of sterile water for injection, USP, which is transferred by two-way needle into the lyophilized powder for reconstitution, and the reconstituted vial infused over 5-10 minutes, at 80 IU/kg (per pre-pregnancy weight) at delivery (or epidural), and days 1 and 2 postpartum.

Tranexamic acid (TA, Cyclokapron®) is an FDA-approved anti-fibrinolytic agent for the treatment or prevention of bleeding in bleeding disorders. It is an intravenous agent supplied as a sterile, unpreserved, colorless solution administered in single-dose polymeric bags containing 1000 mg tranexamic acid in sodium chloride in 100 ml and given at a rate of 1 ml/ minute, at 1 g within 3 hours after delivery.

Trial Arms	
Arm A	rVWF 80 IU/kg at delivery (or epidural), and day 1, 2 plus TA 1 gm IV within 3 hours after delivery
Arm B	rVWF 80 IU/kg at delivery (or epidural) and day 1, 2 alone

Study Duration:

[figure not shown]
This is a 8-week inpatient trial in which all subjects will be randomized to one of two treatment arms and followed for 4 weeks.

PROTOCOL SCHEMA

Screening
Week -4
Visit 1

Subjects will be screened at 32-39 weeks' gestation, after signed, informed consent, by inclusion and exclusion criteria; undergo a history, vital signs, and baseline labs: hemoglobin, hematocrit, platelets, Fe, TIBC, ferritin, VWF assays (VWF:RCOF, VWF:Ag, FVIII:C), fibrinogen, and d-dimer, and be randomized to one of two treatment arms.

[figure not shown]
Admission
Childbirth
Week 0
Visit 2

Week 0
Day 0-2
Visits 3-4

On admission for childbirth, subjects will have baseline blood counts, VWF assays, and d-dimer drawn and receive the initial study intervention at delivery (or epidural), and on days 1 and 2 postpartum. At 1 day and 2 days postpartum, lochial blood loss by PBAC, blood products, transfusion, and concomitant medications will be reviewed; and blood counts, VWF assays, fibrinogen, and d-dimer will be drawn.

Week 3
Visit 5

ABSTRACT

This is a single-center randomized phase III pilot clinical trial, the **VWD-Woman Trial**, in which 20 pregnant women with von Willebrand disease, defined as VWF:RCo <0.50 IU/ml (historic) and previous bleeding history, are enrolled. Subjects will include women with VWD age 18 years of age and older, excluding those who have a bleeding disorder other than VWD. Once enrolled, subjects who meet all of the inclusion and none of the exclusion criteria will be randomized to recombinant Von Willebrand factor (Vonvendi, rVWF[®]) with Tranexamic Acid (TA, cyclokapron[®]) or recombinant Von Willebrand factor (Vonvendi, rVWF[®]) alone to prevent postpartum hemorrhage after a vaginal or caesarean section. The primary endpoint is quantitative blood loss (QBL) collected by a labor suite nurse at delivery, and secondary endpoints include safety assessment for postpartum lochial blood loss by Pictorial Blood Assessment Chart (PBAC), transfusion, blood products, thromboembolic events, and hysterectomy within 21 days; and mechanism of PPH reduction by VWF assays (VWF:RCo, VWF:Ag, VIII:C), fibrinogen, and d-dimer. Blood draws are at 5 time points, including at 32-39 weeks' gestation (screening), on admission for childbirth, and at 1 day, 2 days, and 21 days after delivery. The VWD-Woman Trial is considered greater than minimal risk as study drugs are given at delivery and special coagulation studies are obtained.

Principal Investigator: [name], DO

Co-Investigators: [name]

Protocol Title: The Von Willebrand WOMAN (VWD-Woman) Trial: A Phase III Randomized, Pilot Trial Comparing Recombinant von Willebrand Factor (rVWF, Vonvendi®) plus Tranexamic Acid (TA, Cyclokapron®) vs. rVWF, Vonvendi® alone to Prevent Postpartum Hemorrhage in Women with Von Willebrand Disease

1.0 Objective and Specific Aims

The purpose of this 8-week single center, randomized, open-label pilot phase III trial is to prevent postpartum hemorrhage in women with von Willebrand disease. This 8-week open-label, randomized, controlled single-center trial will compare recombinant von Willebrand factor (rVWF, Vonvendi®) plus Tranexamic Acid (TA Cyclokapron®) vs. rVWF, Vonvendi® alone to reduce postpartum hemorrhage (PPH) in women with VWD. Both drugs are approved by the FDA to prevent and treat bleeding in individuals with von Willebrand disease. In this trial, subjects will be pregnant women age 18 years and older with VWD, defined as VWF:RCo <0.50 IU/dL and past bleeding history. The research is considered greater than minimal risk as it involves study drugs at delivery, and special coagulation studies are obtained. Blood loss at delivery will be by quantitative blood loss (QBL) at delivery calculated by a labor suite nurse, and postpartum blood loss will be lochial blood loss by pictorial blood assessment chart (PBAC), validated for postpartum blood loss. The primary endpoint is quantitative blood loss (QBL) during C-section and vaginal delivery and calculated by a labor suite nurse. The secondary endpoints will include i) assessment of safety by lochial blood loss by pictorial blood assessment chart (PBAC) validated for postpartum blood loss, transfusion, blood products, thromboembolic events, and hysterectomy within 21 days of delivery; and ii) assessment of the mechanism of PPH reduction by von Willebrand assays (VWF:RCo, VWF:Ag, FVIII:C), coagulation assays (fibrinogen, and d-dimer measured at screening (32-39 weeks') gestation (screening), on admission for childbirth, and at 1, 2, and 21 days postpartum. The trial will assess PPH hemorrhage reduction after each subject completes the 8-week trial.

2.0 Background and Significance

2.1 Significance

Von Willebrand disease (VWD) is the most common congenital bleeding disorder, occurring in 1% of the population.¹ It is caused by quantitative or qualitative deficiency of von Willebrand factor (VWF). VWF is a multimeric plasma glycoprotein which serves both as a carrier molecule for factor VIII and as an adherent protein that mediates platelet adhesion to damaged vascular endothelium.^{2,3} The bleeding in VWD is primarily mucosal, including bruising, epistaxis, menorrhagia, and postoperative bleeding, and, in women of child-bearing years, reproductive tract bleeding, including postpartum hemorrhage (PPH).^{3,4} Women with VWD have a 1.5-fold greater odds of PPH than controls,⁵ with an incidence of 5.5%.⁶ Over one-quarter of women with VWD and PPH are anemic, or twice as many as non-VWD women with PPH, and are more likely to require a red blood cell transfusion.⁶ When severe, < 7 g/dL, anemia is refractory to routine iron supplementation and associated with a 2-fold greater odds for maternal death.⁷ These data suggest PPH is a significant cause of maternal morbidity and mortality.

Postpartum hemorrhage is the leading cause of maternal death in the world and accounts for one third of maternal deaths in the United States. Defined as blood loss exceeding 1000 mL in first 24 hours with vaginal delivery or cesarean delivery,⁸ PPH peaks in the first 2-3 hours postpartum, a time during which there is early activation of the fibrinolytic system, with a 2-fold increase in TPA (tissue plasminogen activator).⁹ Overall, while uterine atony is the major cause of PPH, accounting for 63% of PPH cases,¹⁰ and uterotonic agents are effective in reducing PPH,¹⁰ but in 37% they may fail.

Current guidelines indicate that management of postpartum hemorrhage should include hemostatic agents, including antifibrinolytic agents, e.g. tranexamic acid, which is an inhibitor of plasmin-mediated

fibrinogen and fibrin breakdown, along with transfusion support including blood and plasma products.¹⁰ Tranexamic acid (TA) has been shown not only to reduce blood loss after elective surgery¹¹ but also to reduce blood loss and mortality after trauma (CRASH-2).¹² In the WOMAN trial of over 20,000 women with postpartum hemorrhage, there was a significant reduction in bleeding and mortality from bleeding, when tranexamic acid (TA, Cyclokapron) was given at a dose of 1 gm IV within three hours of delivery.¹³ This benefit was associated with a reduction in d-dimer,¹⁴ and no adverse effects, in particular, no thrombotic complications.¹³ Moreover, subsequent studies, including a meta-analysis of 25 trials showed that when TA was given preventively before vaginal and cesarean delivery, it reduced the rate of PPH, with no thrombosis.¹⁵⁻¹⁷ No randomized trial has evaluated tranexamic acid when given within 3 hours of delivery in preventing PPH in women with VWD. Clearly, future trials are needed to determine the role of TA in preventing PPH in VWD.

In women with VWD, hemostatic support with clotting factor is the current approach to PPH prevention. Based on expert U.S., NHF and European guidance, a VWF level > 0.50 IU/dL is recommended before epidural delivery.^{10,19-27} While some advocate a dose of VWF 50 IU/kg at delivery,^{10,19-21} there is no specific guidance regarding the optimal dose or duration to prevent PPH, although some advocate avoiding DDAVP which may be associated with hyponatremia due to fluid loss and replacement at delivery.¹⁹ Yet, a dose of 50 IU/kg is lower than that recommended for other surgical procedures, 80 IU/kg,¹⁹⁻²¹ attributed, in part, to fear of increasing the risk of thrombosis in the postpartum period. Yet, thrombosis is uncommon with VWF concentrate. In published studies, trials, and clinical experience over the last two decades, thrombosis occurs in less than 0.4%, even when doses as high as 100-200 IU/kg are given.³⁶ Yet, up to one-third of women with VWD develop PPH despite factor replacement.²² In a prospective observational study, of women with VWD, even when VWF concentrate was given before and after delivery, VWF levels were lower and blood loss was greater in women with VWD than in controls,²³ and VWF levels peaked earlier than controls, at 4 hours postpartum, rapidly declined, and remained lower than controls for 3 weeks.²³ A more recent observational study found, however, no difference in PPH between those receiving 50 IU/kg and 80 IU/kg, the standard dose for surgery.²⁷ Finally, although it is known that third trimester VWF levels are inversely related to PPH risk,²² and lower pre-pregnancy VWF and higher pre-pregnancy and third-trimester body weight are associated with PPH,²⁴ there are no established predictors of PPH. While the optimal VWF level and duration of treatment are not known, it is clear that 50 IU/kg is insufficient to prevent PPH.

Why there is increased blood loss and lower VWF levels at delivery in women with VWD, despite VWF treatment, remains unknown. The current recommended VWF dosing, 50 IU/kg, does not take into account the 1.5-fold increase in blood volume.²⁸ Yet, while not used in pregnant women with VWD, volume-based dosing, rather than weight-based factor dosing is routinely used in children and obese adults with hemophilia.²⁹ Yet, during pregnancy, the physiologic increases in cardiac output, extracellular fluid, renal blood flow, and glomerular filtration rate accelerate drug clearance,^{30,31} and is the basis for blood volume-based dosing for a number of drugs in pregnancy.³² Finally, the physiologic fibrinolysis that occurs in the first three hours postpartum may contribute to greater bleeding in the woman with a bleeding disorder such as VWD.

Therefore, we *hypothesize* that rVWF 80 IU/kg IV, a dose safe and effective in treatment and prevention of VWD bleeding, standardly administered for surgery, and appropriate for the 1.5-fold increase in blood volume in pregnancy, when given before and on day 1 and day 2 after delivery, *plus* tranexamic acid 1 gm IV, a dose safe and effective in treatment and prevention of postpartum hemorrhage and mortality related to PPH, will be superior to rVWF alone in reducing PPH in women with VWD. This trial will help to enhance our understanding of the coagulopathy and mechanism PPH in VWD and, will be consistent with the goals and objectives of Healthy People 2020, to develop safer, more effective products for treatment of VWD.

2.2 Significance. By studying the safety and biologic effects of rVWF with TA vs. rVWF alone, we hope to

determine in this pilot study the feasibility of the VWD-Woman trial, the purpose of which is to reduce postpartum hemorrhage in women with VWD. Specifically, if we demonstrate the clinical hemostasis, and safety and tolerability of VWD with or without TA, in reducing PPH women with VWD, this would provide evidence that our clinical trial is feasible and biologically plausible. Finally, the findings of this study will potentially provide new information to determine feasibility for use in a future prospective phase III randomized clinical trial to prevent postpartum hemorrhage in women with von Willebrand disease, and promote blood product safety, consistent with the goals of Healthy People 2020.

3.0 Research Design and Methods

3.1 Drug/Device Information

Recombinant VWF (rVWF, Vonvendi®) is an FDA-approved recombinant von Willebrand factor indicated for the treatment and prevention of bleeding episodes in individuals with von Willebrand disease, approved by the FDA for treatment or prevention of bleeds in VWD. rVWF is produced by DNA technology. It is synthesized by a genetically engineered Chinese hamster ovary (CHO) cell line that co-expresses both VWF and FVIII genes.¹⁰ It is manufactured and formulated in the absence of animal or other human plasma proteins, thus eliminating the theoretical risk of transmissible agents and other blood-borne pathogens. It contains ultra-large and high molecular weight multimers (HMWM) of VWF that are essential for platelet plug formation.^{1,2} with no exposure to ADAMTS13 during the production process and thus contains intact HMWM and ULM.¹⁰ rVWF has been shown to be safe and hemostatically effective in types 1, 2, and 3 VWD for treatment of bleeds, with 96.9% rating bleed control excellent or good, and was well tolerated, with no associated with any cardiac symptoms, and there were no thrombotic or severe allergic events, or antibodies to VWF or FVIII.^{11,12} rVWF for injection is formulated as a sterile, non-pyrogenic lyophilized white to off-white powder for intravenous injection after reconstitution. The product contains tri-sodium citrate-dihydrate, 15 nM, glycine 15 mM, mannitol 20 g/L, trehalose-dihydrate, 10 g/L, and polysorbate 80, 0.1 g/L. It is available in single-dose vials for reconstitution containing nominal 650 or 1300 international units VWF:RCo. After reconstitution of the lyophilized powder and filtration/withdrawal into a syringe, all dosage strengths yield a clear, colorless solution free of particles. The 650 IU/vial is reconstituted with a 5-ml vial of sterile water for injection, USP; the 1300 IU/vial is reconstituted with a 10-ml vial of sterile water for injection. The resulting solutions for the individual 650 IU/vial and 1300 IU/vial have a pH of 7.3. A two-way needle will allow transfer of the diluent into the lyophilized powder for reconstitution and slow infusion over 5-10 minutes. Storage of rVWF post-reconstitution should be at room temperature not to exceed 25°C (77°F) for up to 3 hours.

Tranexamic acid (TA, Cyclokapron®) is an FDA-approved antifibrinolytic agent indicated for the treatment of bleeding in individuals with fibrinolysis and has been used for years with a long safety profile in subjects with bleeding disorders. Tranexamic acid in sodium chloride is supplied for injection as a sterile, unpreserved, colorless solution in a single-dose polymeric bag containing 1,000 mg of tranexamic acid in 100 mL (10 mg/mL), sealed with a twist off port and oversealed in an aluminum pouch. It is infused at 1 mL per minute, or over 10 minutes. It is stored at 20°C to 25°C (68°F -77°F).

Once a subject is consented and identified as eligible for this trial, a unique subject number will be assigned to each subject by the GSPH Data Center, Pittsburgh PA. Study drug dosing will be given by Magee Women's Hospital research staff. Both drugs will be provided, by Takeda funding, through the Magee pharmacy per randomization code to subjects participating in this study. Once a subject is identified as eligible for the study, she will be assigned a unique ID number and randomized by the GSPH Data Center. The randomization code will be linked to study drug, rVWF and TA, and the accession number placed on the drug vial or bag, in agreement with the accession number assigned to each study subject. Each study drug will be labeled with storage, lot number, stability, production and expiration dates by the Magee Inpatient Research Pharmacy.

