The goal of the current study will be to obtain preliminary information on the safety and efficacy of rVWF given at 80 IU/kg at delivery and day 1, day 2, with or without TA 1 gm IV within 3 hours of delivery in reducing postpartum hemorrhage in 20 pregnant VWD subjects. If the study recruitment, randomization, drug administration, data collection and management are feasible, then the large, multicenter phase III trial will be initiated. As both drugs are FDA-approved and have been previously used in VWD patients without adverse effects, we anticipate none during the study. If any subject experiences any grade 3 or higher treatment-related toxicity, blood loss, allergic reaction (fever, chills, hives, tachycardia, chest discomfort), or thrombosis, the decision to continue the study will be made by a local Data Safety Monitoring Committee.

DOSING SCHEMA

Study Arms	No. Subjects	Study Drug(s) at Delivery	Study Drug Postpartum
Arm A	10	rVWF 80 IU/kg + TA 1 gm	rVWF 80 IU/kg days 1 and 2
Arm B	10	rVWF 80 IU/kg	rVWF 80 IU/kg days 1 and 2

rVWF is a single-dose IV infusion given over 5-10 minutes. TA is a single-dose IV infusion given over 10 minutes.

Screening Procedures. Following informed consent, subjects will be screened at the Hemophilia Center of Western PA, by medical history, physical examination, vital signs (height, weight, blood pressure, respirations, heart rate, temperature), and baseline laboratory studies within 3 weeks of the escalating dose study. Baseline labs will include **VWF assays** (VWF:RCo, VWF:Ag, FVIII:C); **coagulation tests** (fibrinogen, d-dimer), **blood counts** (hemoglobin, hematocrit, platelet count); and **iron tests** (Fe, TIBC, ferritin). All tests will be drawn at screening (32-39 weeks' gestation), and all tests except for the iron tests will be drawn on admission for childbirth, at day 1, day 2, and day 21 postpartum. Blood draws will be performed on day 0 pre-delivery by the Magee Labor and Delivery unit as soon as the IV is started. Subsequent blood draws on day 1 and day 2 will be coordinated through HCWP research team. The total blood draw is 49 cc (~2.5 tbsp), including 13 cc (~1 tbsp) at screening; and 9cc (~0.6 tbsp) at the remaining 4 blood draw draws. See Appendix 1.

Up to 30 subjects will be screened to assure 20 subjects are enrolled. Subjects will be randomized to rVWF + TA vs. rVWF alone at delivery. Subjects will receive only the study drug(s) to which they are

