randomized, by slow push intravenous infusion. (See Dosing Schema, above). The dose of rVWF will be 80 IU/kg given intravenously over 5-10 minutes at delivery and on day 1 and day 2 postpartum. The dose of TA will be 1 gm (100 mg/mL) given intravenously at an approximate rate of 1 mL/min within 3 hours of delivery. Subjects on Arm A will receive: rVWF 80 IU/kg IV at delivery and on day 1 and day 2 postpartum plus TA 1 gm IV within 3 hours of delivery. If bleeding continues after 30 minutes of the first TA dose, a second dose of TA 1 gm IV will be given. Subjects on Arm B will receive: rVWF 80 IU/kg IV at delivery and on day 1 and day 2 postpartum. rVWF will be given by IV infusion by the Magee research nurse just before delivery, and day 1 and day 2 postpartum. TA will be given by IV infusion by the Magee research nurse within 3 hours of delivery. Efficacy assessment, quantitative blood loss (QBL) at delivery, will be determined at delivery, and obtained from the medical record. Safety assessments, including lochia blood loss by pictorial blood assessment chart (PBAC), blood products, transfusion, and other medications will be recorded on the patient diary at 1 day, 2 days, and 21 days postpartum. After each infusion at delivery and on day 1 and day 2 postpartum, any symptoms, allergic reaction, or thrombosis will also be recorded.

The total blood draw for the entire study is 49 cc (~3 tbsp), including 13 cc (~1 tbsp) at screening (32-39 weeks' gestation), and 9 cc (~ ½ tbsp) each on admission for childbirth, at 1 day, 2 days and 21 days postpartum. Blood samples collected during this study will be stored indefinitely at the hemophilia Center of Western PA (HCWP). If other studies are planned, the subject will be re-consented for approval. The stored samples will be under the control of [name]. There is no plan to use the samples for genetic tests or other tests nor to make them available to secondary investigators.

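### The tranexamic acid bag, rate and duration are incompatible: 100 mL at 1 mL/min takes 100 minutes, not 10, and 10 minutes delivers only 100 mg of the 1 g dose

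*Combined protocol and SAP*

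**What the plan says.** Four places in the combined protocol and SAP specify how TA is given.

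- **Synopsis, Description of Study Intervention:** single-dose bags "containing 1000 mg tranexamic acid in sodium chloride in 100 ml and given at a rate of 1 ml/ minute", with the dose set "at 1 g within 3 hours after delivery". No duration is given.
- **Section 3.1, Drug/Device Information:** a single-dose bag with "1,000 mg of tranexamic acid in 100 mL (10 mg/mL" as its stated content and strength, followed by "It is infused at 1 mL per minute, or over 10 minutes".
- **Section 3.2, Dosing Schema:** Arm A receives "rVWF 80 IU/kg + TA 1 gm" at delivery, with the note "TA is a single-dose IV infusion given over 10 minutes".
- **Section 3.2, text after the Dosing Schema:** "The dose of TA will be 1 gm (100 mg/mL) given intravenously at an approximate rate of 1 mL/min within 3 hours of delivery".

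Section 3.2, there and under Study Visit 2, also allows a second 1 g dose in Arm A if bleeding persists 30 minutes after the first.

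On the pilot's purpose, Section 3.2 states: "If the study recruitment, randomization, drug administration, data collection and management are feasible, then the large, multicenter phase III trial will be initiated". Section 3.3, including its sample size paragraph, likewise lists study drug administration among the procedures by which feasibility is judged.

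**The concern.** Section 3.1 joins a rate and a duration with the word *or*, as if they were two ways of stating one infusion. For the bag described just before, they differ ten-fold. The other places do not settle the matter: one agrees with the rate, one with the duration, and one brings in a different concentration.

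TA is the only drug that differs between the arms, and these figures govern its administration in all 10 planned Arm A subjects. A nurse who sets the written rate on the described bag gives a 100-minute infusion; one who follows the dosing schema gives a 10-minute infusion. The rationale in Sections 2.1 and 3.2 rests on fibrinolysis in the first three hours after delivery, so a ten-fold difference in infusion time is not trivial. Because drug administration is part of the feasibility judgement, the plan also needs one specification against which an infusion can be called correctly given.

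**Working it through.** **Inputs**

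- Dose: 1,000 mg (synopsis; Section 3.2).
- Concentration: 1,000 mg / 100 mL = 10 mg/mL (synopsis and Section 3.1), or 100 mg/mL (Section 3.2 text).
- Rate: 1 mL/min (synopsis, Section 3.1; approximate in the Section 3.2 text).
- Duration: 10 minutes (Section 3.1; Dosing Schema).

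**Formulas**

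- Volume = dose / concentration
- Time = volume / rate
- Amount delivered = concentration × rate × time

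**Can the stated 10 minutes be reproduced?** Only with the 100 mg/mL figure:

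- Volume: 1,000 / 100 = 10 mL
- Time: 10 / 1 = 10 minutes, delivering the full 1,000 mg

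**The same check with the bag described in the synopsis and Section 3.1:**

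- Volume: 1,000 / 10 = 100 mL
- Time at 1 mL/min: 100 / 1 = 100 minutes, a dose rate of 1,000 / 100 = 10 mg/min
- Delivered in 10 minutes at 1 mL/min: 10 × 1 × 10 = 100 mg, or 10% of the dose, leaving 1,000 − 100 = 900 mg (90%)
- Needed for 1 g in 10 minutes: 100 mL / 10 min = 10 mL/min, a dose rate of 1,000 / 10 = 100 mg/min

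| Concentration | Volume for 1 g | Time at 1 mL/min | Given in 10 min at 1 mL/min | Rate for 1 g in 10 min |
|---|---|---|---|---|
| 10 mg/mL (synopsis, 3.1) | 100 mL | 100 min | 100 mg | 10 mL/min |
| 100 mg/mL (3.2 text) | 10 mL | 10 min | 1,000 mg | 1 mL/min |

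The synopsis agrees with itself but implies 100 minutes. The Section 3.2 text agrees with the Dosing Schema but not with the bag. Section 3.1 contradicts itself.

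**Two consequences of the 100-minute reading**

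- It would take up 100 / 180 = 56% of the three-hour period. To finish inside that period, the infusion would have to start within 180 − 100 = 80 minutes of delivery.
- If the 30-minute clock for the second dose runs from the start of the first infusion (an assumption, as the plan does not say), only 10 × 1 × 30 = 300 mg would have been given when the second gram is considered. With a 10-minute infusion, all 1,000 mg would have been given.

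**The case against.** The strongest reply is that the dose itself never varies. It is 1 g wherever it is stated, and the container is a single-dose bag holding exactly that amount. To give 100 mg, staff would have to discard nine-tenths of the bag against the stated dose. The realistic error is therefore in duration, not in the amount given. This stands: the 100 mg figure is what the Section 3.1 sentence yields when applied literally, not a prediction of practice.

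The documents also lean towards the bag. Two places describe it, one with packaging and storage details, while the 100 mg/mL product is inferred from a single parenthesis. The intended duration can be recovered too: 10 minutes is stated twice and 100 minutes never. Both points are fair. They make one correction more likely than the other, but they do not remove the contradictory figures, and the rate is the figure staff would set.

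Finally, the feasibility criteria mention drug administration only in general terms and set no criterion for infusion rate or time. That limits the feasibility argument without ending it. Dose and three-hour window can be checked as written, but adherence to rate and duration cannot be judged while the two conflict.

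Two possible rescues fail. Calling the rate approximate in Section 3.2 cannot cover a ten-fold gap. Diluting a stronger stock to 100 mL is described nowhere, and 100 mL at 1 mL/min would still take 100 minutes.

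**Conclusion.** The concern holds. The stated bag, rate and duration cannot all be true. The discrepancy is ten-fold in infusion time (100 against 10 minutes), in dose rate (10 against 100 mg/min) and in concentration (10 against 100 mg/mL). This needs nothing beyond the plan's own figures and division.

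Ten minutes is the likely intent, since it is the only duration stated and the Section 3.2 text reproduces it. The documents favour the bag but do not settle which product is dispensed, so they do not show whether the rate or the presentation is the wrong figure. No sample size or analysis figure changes, no effect on quantitative blood loss is claimed, and nothing here shows that anyone was misdosed. These are operative instructions for the drug under comparison, so they should be corrected.

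**What to change.** Ask the pharmacy which TA product is dispensed, then make every section read 1 g over 10 minutes (100 mg/min).

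- **If it is the 1,000 mg/100 mL bag:** change the rate to 10 mL/min in the synopsis, Section 3.1 and the Section 3.2 text; change the concentration in the Section 3.2 text to 10 mg/mL; add the 10-minute duration to the synopsis. Check: 10 mL/min × 10 min × 10 mg/mL = 1,000 mg. Five edits.
- **If it is a 100 mg/mL, 10 mL product:** correct the presentation in the synopsis and Section 3.1; keep 1 mL/min; add the 10-minute duration to the synopsis; leave the Section 3.2 text as it is. Check: 1 mL/min × 10 min × 100 mg/mL = 1,000 mg. Three edits.

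The Dosing Schema stays as written in both cases. The cost is one pharmacy query and wording changes, with no change to sample size or analysis.
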